## Recruitment Table:

## Feasibility of recruitment:

There is an emphasis on feasibility of the trial recruitment to ensure we reach our target sample size, especially considering the 9-months commitment requirement for each participant. Below is a step-by-step description of our recruitment strategies to demonstrate feasibility:

- Prior to submission of the current application, 3 participants were already identified and were willing to participate in our preliminary work.
- We will contact every SCI physician, nurse and rehabilitation staff (including those at the Spokes sites) about our ongoing protocol through our weekly clinical rounds, grand rounds, and friendly e-mail reminders.
- We will send an email blast through our secured network to our 13 Spokes sites and encourage them to refer potential participants to our research team.
- We will send electronic flyers and the PI will present at our SCI monthly meetings, PVA monthly meeting, SCI quarterly newsletters, hub and spoke annual conferences, and SCI national Chief teleconference meetings.
- Our SCI&D service has a designated wheelchair van that we have been using on a regular basis for transportation of our participants back and forth during the course of clinical trials, assuming they reside in the Richmond area. This accessible transportation has encouraged several participants to be enrolled in previous VA trials and we plan to use this method too to encourage participation in the proposed trial; they will only need to come to the center at the beginning of the trial, mid-term and at the end of the trial for imaging and blood work.

## Process for obtaining informed consent:

The PI will seek informed consent from eligible participants with an IRB approved consent form. Determination of a participant's capacity to consent will be made by the PI. Input may be solicited from participant's SCI Provider on record, who knows the potential participant well. Potential participants will be given full verbal explanation of the study protocol by the PI. If they voice an interest in the study, they will receive the written consent form and will be provided ample time to consider their participation. All concerns and questions will be answered by the PI. The PI will place emphasis on explaining all study procedures. Family members will be included in the discussion as desired by the participants. Participants will be made aware that participation is voluntary and that they can withdraw at any time with no impact on the care they currently receive or future care from the VA. Participants will be made aware that they can discuss the study participation with their primary SCI Provider, if they chose. Potential participants who take the consent forms home will be given a returned addressed envelope with postage paid in which they can mail back the consent form once signed. All signed consents will be scanned into the VA Computerized Patient Record System (CPRS); a warning note indicating participation in an ongoing research study will be enter in the "Crisis Notes, Warning Notes, Directives (CWD)," section of CPRS to alert CPRS users of participants' enrollment in an ongoing study. In addition to a consent note entered into CPRS for all participants, progress notes of their active participation will also be entered.

### **Limitations and Alternatives:**

- 1)** Those with incomplete SCI (AIS C or D) as they may already be engaging in some weight bearing activities that convey some benefits of bone health, hence may confound the results of the study.
- 2)** Those with marked osteopenia and severe osteoporosis as electrical stimulation and loading to already weakened limbs may increase the risk of sustaining stress fractures.
- 3)** It may be difficult to recruit female Veterans because of limited access as they are fewer in number compared to male Veterans.
- 4)** Ability to recruit and retain the required sample size from current SCI & D registry. However, since the primary mentor had previously recruited and retained almost half of the proposed sample size in the parent study, we anticipate similar success rate.
- 5)** Frequent blood sampling; this procedure has been previously used in IRB approved funded studies without recorded incidence.
- 6)** concerns about **retaining participants** to finish the 9 months study; transportation could be a major impairment to participants' compliance in the SCI population. Fortunately, the study involves limited travel since we are going to use Telehealth (a home-based) approach for the intervention and participants would only be required to travel at enrollment, mid-term and at the conclusion for testing procedures at no financial cost to them. Participants affiliated with the Spokes site can complete these tests at their local VAMC.

## **Risk to Subjects.**

Every effort will be made to minimize potential harm to individuals during the study. There will strict adherence to the protocol's inclusion/exclusion criteria. However, the following may pose potential risk to study participants:

Potential source of risk	Potential Risk	Possibility of occurring
Pressure to skin from weights or skin irritation from weights or during exercise	Pressure injury (break to skin)	Occasionally but no more than usual from daily activities
DXA/MRI	No significant risk This research study will involve exposure to radiation from 2 whole body DEXA scans and MRI with no contrast. This radiation exposure is not necessary for medical care and is for research purposes only. All radiation exposure increases the risk of developing cancer in the future. The total amount of radiation that would be used in this study is equal to less than one day of exposure from natural background radiation. Permission would be obtained from the CVVHCS Radiation Safety Committee, who will review the use of radiation in this research study, involving minimal risk and necessary to obtain the desired research information. Participants will be instructed to tell their Providers if they have participated in other research studies or received any other medical care involving radiation in the recent past.	Unlikely
Phlebotomy	Phlebotomy can cause pain, bruising at the site of the venipuncture, nerve damage, hematoma or infection	Rare
Electrical stimulator/weights (Risk of fracture)	SCI is commonly associated with bone weakness and weight bearing on the participant's limbs while exercising on the rowing machine may increase risk of fracture to already weakened bones.	Rare

Autonomic Dysreflexia (AD)	Weights and exercise to limbs of participants may pose as noxious stimuli that may lead to symptoms of AD (headache, pounding in the head, ringing in the ears, dizziness, blurry vision, sweating, anxiety, flushing, tightness in the chest, stuffy nose, heart flutters, or difficulty breathing), especially in those with cervical level of injury and high thoracic level of injury (T6 and above).	Rare
Falls	Falls could occur during training or transfer unto testing equipment (MRI/DXA table or in the home during transfer to/from wheelchair unto rowing machine.	Rare
Risk of Fracture	SCI is commonly accompanied by bone weakness and weight bearing on the participants' limbs may increase their risk of sustaining stress/low impact mechanical fracture.	
Medication (Vitamin D)	Vitamin D toxicity can lead to hypercalcemia and kidney stones. To reduce this risk participant's serum level of 25(OH)D will be monitored closely and re-assessed at mid-term and at end of intervention. Hypercalcemia is usually not seen unless the D level is > 100 ng/ml.	Rare
Rowing equipment	It is possible that the rowing machine may malfunction or cause stress injury to the weakened limbs	Rare
Implanted device malfunction due to use of MRI	Implanted metallic device may pose risk for using MRI device, for example, implanted stimulator or intrathecal pump device may malfunction following MRI exposure. These are reprogrammable if they occur.	Rare

### **Protection Against Risk:**

Every effort will be made by the PI and the study team to minimize potential risks. Any procedures will be carried out in accordance with established standard operating procedures and necessary precautions will be taken to mitigate any potential risk. There will be strict adherence to the inclusion & exclusion criteria for the protocol. Appropriate

health screening and strict compliance with the established exclusion criteria will minimize attrition due to medical reasons. Participants will be closely monitored by the PI at all visits. All participants will be provided a 24-hour contact information for the PI and instructed to call for any concerns. Unscheduled visits may be performed if required for evaluation of safety. If a participant exhibits an adverse event, more frequent visits may be necessary.

- Protection of skin integrity during intervention

Skin will be closely inspected with the help of the caregivers for dose with caregivers, otherwise, by the PI via the webcam during each intervention session to ensure maintenance of skin integrity.

- Protection from risk associated with transfers

To minimize risk, a caregiver will be available to assist in all transfers and provide a sliding board or any other assistive devices needed for those without good upper body strengths. For those without caregivers, safe transfer techniques would have been validated prior to enrollment.

- Protection from risk associated with radiation exposure

To minimize risk, only the required scans will be performed. Testing will be performed early in the day and after lower extremity elevation for at least 30 minutes to minimize lower extremity edema. An overhead lift system is installed in the exercise lab to ensure safe transfers on and off the DXA scanner.

A possible health problem seen with radiation exposure is the development of cancer later in life. This extra cancer risk is higher at younger ages and for girls and women. The extra lifetime risk of dying of a fatal cancer due to the radiation exposure from this research is very low. At such low radiation exposures, scientists disagree about the amount of risk. These estimates are very uncertain, and there may be no extra risk at all.

- Protection from falls during transfers

Falls could occur during transfers with sliding board or portable lift from bed to wheelchair and from wheelchair unto intervention equipment (rowing machine). This requires careful use of equipment. To avoid this kind of accident, transfer techniques will be reviewed with participants and caregivers (where applicable) at the beginning of the study. However, this rarely occurs after a Veteran has successfully completed rehabilitation treatment post injury.

- Protection against risk of fracture

Every effort will be taken to minimize possible bone fracture; DXA scan will be performed as detailed earlier prior to enrollment in the trial. Persons with T-score less than -2.5 SD at the hip joints or with bone mineral density less than 0.6 gm/cm^2 at the knee joints will be excluded from the trial.

- Protection from autonomic dysreflexia

Blood pressure (BP) will be monitored closely during the entire intervention and established AD protocol followed should participant experience AD symptoms (patients and caregivers usually receive training on AD management at home, during their rehabilitation course). Any significant rise in BP greater than 20 mmHg above resting BP, the intervention will be suspended immediately and AD protocol instituted. The PI will remain on video connection until AD symptoms resolved and participant returns to normal state.

- **Protection against medications adverse effects**

Medication associated with the current trial can cause allergic reactions, such as, rashes, nausea, vomiting, and hypercalcemia. The PI will obtain allergy history (prior reactions) and monitor the patient and blood parameters closely during the course of the trial to avert any serious drug reaction.

**Study removal criteria may include:** Participants may be withdrawn from the study by the research team for the following concerns:

1. New medical diagnosis of carcinoma of the breast or prostate as these would may have bone health implications. Deep venous thromboembolism as this will hinder intervention and may increase risk of pulmonary embolism; stroke, hypertension, serious heart problems, heart failure, myocardial infarction, ventricular arrhythmia, exertional chest pain, insulin dependent diabetes, hypercholesterolemia, hypertriglyceridemia, impaired liver function, hypercalcemia, or significant renal dysfunction.
2. Hospitalization for acute medical problems (e.g. Liver enzymes (AST / ALT) >1.5 times normal upper limit).
3. Serum calcium greater than 16mg/dL or symptoms of hypercalcemia
4. Severe peripheral edema, classified as 2+ or higher
5. Any SAE that the SCI physician, [name], deems necessary for withdrawal for participant's safety.

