**Exclusion Criteria:** Participants with any of the following pre-existing medical conditions will be excluded from the trial: **1)** neurological injury other than SCI,(e.g. cauda equina or distal conus injuries resulting in limb or sacral areflexia; **2)** Unhealed fracture in either lower or upper extremities; **3)** Severe scoliosis, hip knee range of motion (ROM)  $>$  20 degrees. or flexion knee contractures **4)** Uncontrolled hypertension (BP  $>$ 140/90 mmHg) and severe orthostatic hypotension (BP drop  $>$  20 mmHg) or inability to maintain a sitting position ; **5)** Other medical conditions like cardiovascular disease, uncontrolled type II DM, insulin-dependent DM, or symptomatic urinary tract infection; **6)** severe hypercalcemia (defined as Serum calcium  $>$ 16 ng/mL); **7)** anti-coagulant or anti-platelet therapy, including aspirin. **8)** pacemakers and/or defibrillator devices in place, metallic implants, shrapnel or bullets in the vertebral column, or other contraindications for MRI; **9)** DXA total body-score  $<$  -2.5, knee BMD scores  $<$  0.6 g/cm^2; **10)** Participants with spasticity that is severe or adjudged a contraindication by the site Physician or limited ROM will be excluded. **11)** Pressure ulcer of the trunk, pelvic area, or lower extremities of  $\geq$  stage 3; **12)** Psychopathology history that may conflict with study objectives; **13)** Potential participants who are not wheelchair users and cannot transfer with sliding boards or portable lifts.**14)** serum Vit. D  $>$  40 ng/mL; **15)** abnormal/elevated calcium level **16)** pregnancy (female participants). Medically accepted birth control is required to enter this study. This may include, but is not limited to, birth control pills, IUD's, condoms, diaphragms, implants, being surgically sterile, or being in a post-menopausal state. A blood pregnancy test will be conducted to rule out any pregnancy before the study at the McGuire VAMC. The test will be repeated every month during the course of the study. The blood samples will be sent to the McGuire VA pathology lab for analysis. **17)** Any condition that, in the judgment of the principal

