**Dual energy x-ray absorptiometry (iDXA):** iDXA will be used to measure bone composition including regional and total *Fat Mass (FM)*, *Fat Free Mass (FFM)*, cortical porosity, and BMD. Total body and regional scans will be performed using an iDXA scanner (Lunar Inc., Madison, WI) bone densitometer to determine regional BMD and total body T-score, Total hip BMD and knee BMD scores (Total body T-score less than -2.5. Total hip BMD T-scores < -3.5 and knee BMD scores of less than 0.6 g/cm^2, will be excluded). Testing is performed after lower extremity elevation for at least 20 min to minimize fluid shift. Scanning and analysis is certified by DXA operator. The participant is assisted to lie on a padded table with both legs strapped proximal to the knees and ankles. The arms and legs are properly aligned to allow participant to lie still for 10 min during the scan. Total and regional FM and FFM are determined with DXA software in order to control for confounding variables; fat mass and BMF may influence bone health. The coefficient of variability of two repeated scans is < 3%.

**Specific aim 2:** We will assess bone remodeling with the following bone biomarkers: *BALP*, *P1NP* and *CTX*, 25(OH)D, PTH, renal panel, magnesium and calcium levels at baseline, 4.5 mos and 9 mos. HgbA1c will be obtained prior to and post intervention to determine glucose uptake benefit resulting from the intervention. Blood samples not exceeding 10 mls will be obtained after 8-10 hours overnight fasting. Samples will be processed at CVHCS Clinical Pathology Laboratory or Quest diagnostic depending on negotiated cost. All tests will be performed at the VAMC and participants transportation to and from test will be sponsored.

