**Inclusion of women Veterans:**

There is inherently gender disparity in the Veteran population based on the fact that more men than women tend to join the military. However, the study team will make every effort to recruit female Veterans but may be limited due to scarcity of female Veterans with SCI.

**Exclusion criteria:** Every effort will be made to ensure participants' safety and any participant with active medical condition that may confound the result of the trial will be excluded from participation.

Potential participants will be excluded if they exhibit any of the following:

1. Neurological injury other than SCI
2. Older than 65 years of age as they may likely have considerable amount of bone loss at that age.
3. Have severe osteoporosis because loading porous/fragile bone by electrical stimulation may result in bone fracture.
4. Those classified as AIS C & D, as they may already be engaging in weight bearing activities that may confound the results of this trial.
5. Unhealed or unstable fractures in either lower or upper extremities.
6. Severe scoliosis, deformities in the hip, knee, or ankles OR impaired range-of-motion, as these could be a barrier to safe positioning on the rowing machine, and on MRI or DXA tables.
7. No caregiver or family member/significant other, willing to help with placing weights and positioning participants' lower extremities on the rowing machine.

8. Untreated or uncontrolled hypertension (systolic blood pressure (BP) > 140 mmHg; diastolic BP > 90 mmHg), and/or sudden hypotension upon transferring from bed to wheelchair, characterized by a drop in BP by 20 mmHg (especially in persons with tetraplegia) or heart rate > 100 beats per minute.
9. Anti-coagulation or anti-platelet therapy (including aspirin)
10. Implanted pacemakers, implanted defibrillator devices or any metallic implants including knee or hip implants.
11. Presence of bullets in vertebral column or shrapnel anywhere in the body that may interfere with MRI procedure.
12. Other medical conditions including cardiovascular disease, uncontrolled type II DM, active deep vein thrombosis (DVT), uncontrolled autonomic dysreflexia, use of insulin for DM management, pressures injuries of stage 3 or higher, or active urinary tract infection.
13. Severe hypercalcemia (serum calcium > 16mg/dl), stage III-V kidney disease, post-menopausal or estrogen dependent female, and men undergoing anti-androgen therapy or are post orchiectomy.

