14. DXA total body T-score less than -2.5. Total hip BMD T-scores < -3.5 and knee BMD scores of less than 0.6 g/cm^2.
15. Untreatable severe spasticity bearing on potential participants' activities of daily living, such as transfers from bed to wheelchair or maintaining position in wheelchair.
16. Any psychiatric illness confounding judgment or cognitive impairment in participant or caregiver who is expected to help participant in the trial.
17. Those with prosthetic lower limbs
18. Any condition that, in the judgment of the PI or other medical Providers, preclude safe participation in the study and/or has the potential to expose/increase participant's risk of infection.
19. Unable to tolerate increasing either electrical stimulation current or weights to the lower legs for any reason.

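### The hip T-score exclusion contradicts itself: below -2.5 in the fracture-protection text, below -3.5 in the iDXA paragraph and the Human Subject list, and no hip limit in the Research Design list

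*Combined protocol and SAP*

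**What the plan says.** Four places in the current text set bone-density exclusions.

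- **Protection Against Risk, risk of fracture.** Candidates are excluded if they are "Persons with T-score less than -2.5 SD at the hip joints or with bone mineral density less than 0.6" g/cm² at the knee. The same paragraph says "DXA scan will be performed as detailed earlier prior to enrollment in the trial".
- **Research Design and Methods, iDXA paragraph.** A total body T-score below -2.5 excludes, followed by "Total hip BMD T-scores < -3.5 and knee BMD scores of less than 0.6" g/cm².
- **Human Subject Section, Exclusion criteria, item 14.** "DXA total body T-score less than -2.5. Total hip BMD T-scores < -3.5 and knee BMD scores of less than 0.6" g/cm². The list opens with "Potential participants will be excluded if they exhibit any of the following".
- **Research Design and Methods, Exclusion Criteria, item 9.** A "DXA total body-score" below -2.5 and a knee value below 0.6 g/cm², with no hip limit. This list opens with "Participants with any of the following pre-existing medical conditions will be excluded from the trial".

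Other passages touch on bone fragility without giving a hip value. Item 3 of the Human Subject list is "Have severe osteoporosis because loading porous/fragile bone by electrical stimulation may result in bone fracture". Item 2 under Limitations and Alternatives raises marked osteopenia and severe osteoporosis as a fracture concern. Item 17 of the Research Design list and item 18 of the Human Subject list let the investigator exclude on judgment.

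**The concern.** The protocol offers the hip limit as a safeguard against fracture in people whose legs will be stimulated and loaded. Risk to Subjects and Protection Against Risk both promise strict compliance with the eligibility criteria, but the hip criterion has two printed values and is missing from one list. Two screeners working from different sections could decide differently on the same candidate, each with a printed rule in support. The report would also have no single statement of the hip limit that defined its population. With 20 participants planned, one disputed enrolment is 1/20 = 5% of the sample.

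**Working it through.** The plan gives no figure to reproduce. The check sets the printed rules side by side.

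**Inputs.** h = hip T-score, k = knee BMD in g/cm², b = total body T-score.

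**Rules, with each read as an ordinary list of separate exclusions:**

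- Fracture-protection paragraph: h < -2.5 or k < 0.6
- iDXA paragraph and Human Subject item 14: b < -2.5 or h < -3.5 or k < 0.6
- Research Design item 9: b < -2.5 or k < 0.6

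**Test cases, all with b = -2.0 and k = 0.70, so that only the hip can decide:**

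| Hip T-score | Fracture protection | iDXA / item 14 | Item 9 |
|---|---|---|---|
| -2.5 | not excluded | not excluded | not excluded |
| -3.0 | excluded | not excluded | not excluded |
| -3.5 | excluded | not excluded | not excluded |

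Both printed limits are strict inequalities. The band in which the fracture-protection paragraph disagrees with the iDXA paragraph and item 14 is therefore -3.5 ≤ h < -2.5, for candidates with b ≥ -2.5 and k ≥ 0.6. The knee value of 0.6 is the same in all four places.

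**Does the cross-reference settle it?** No. The fracture-protection paragraph points back to the DXA scan described earlier, and that earlier paragraph carries the -3.5 limit.

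**Does applying everything together settle it?** The union of the rules is b < -2.5 or h < -2.5 or k < 0.6. Every h below -3.5 is already below -2.5, so the limit printed in two places would never decide a case. No available passage says that the union is intended.

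**Minor differences between the two eligibility lists:**

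- *Kidney.* Research Design excludes stage 3b or higher; Human Subject item 13 excludes stages III to V. Stage 3a is treated differently.
- *Calcium.* Research Design item 15 excludes any abnormal or elevated level; Human Subject item 13 excludes only above 16 mg/dL. Research Design item 6 prints 16 in ng/mL. Converted, 16 ng/mL = 16 × 10⁻⁶ mg/mL × 100 mL/dL = 0.0016 mg/dL, smaller by a factor of 16 / 0.0016 = 10,000. The study removal criteria also use 16 mg/dL, so ng/mL is probably a unit slip.
- *Stimulation response test.* The pulse is 450 µs in the Research Design inclusion criteria and 1 ms in Human Subject inclusion item 5, a ratio of 1000 / 450 = 2.22. The documents give no response threshold, so no change in anyone's eligibility is claimed.
- *25(OH)D.* The Research Design inclusion criteria require below 41 ng/mL. Aim 1 and Research Design item 14 exclude above 40. The Human Subject lists have no such limit.

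**The case against.** The strongest reply is that the rules can be applied cumulatively. Both lists exclude on any single criterion, the fracture-protection paragraph is worded as an exclusion, and no passage says that a person with a hip T-score of -3.0 is eligible. On that reading the answer is determinate. This stands in part. A reader might infer that a screening decision in the band cannot be checked against the protocol at all; that goes too far, because the cumulative reading gives an answer. It is only one reading, however, and it empties the -3.5 limit of effect.

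A reader might also take the 'and' in the iDXA paragraph and item 14 literally, so that a low knee value alone would not exclude. The documents do not support this well. The iDXA text runs the limits together as an ordinary list, and item 14 sits under an any-one-excludes opening. The joining word should be tidied, but the finding does not rest on it.

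It can be said that the two detailed DXA statements agree and the outlier is a single risk sentence. That is true, but this sentence is the one offered as the fracture safeguard. If hip joints and total hip were meant as different sites, no passage says so. The judgment clauses allow exclusion within the band but set no limit.

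The kidney and calcium differences can be met by applying every exclusion, and the 25(OH)D point is mainly an omission from one pair of lists. They are editorial beside the hip limit.

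**Conclusion.** The contradiction in the hip limit is real and should be corrected, because the protocol relies on that limit for safety. It is an internal inconsistency in current text. It affects candidates with a hip T-score from -3.5 to just under -2.5 who pass every other criterion.

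The number of such candidates cannot be computed. A reader might infer from the high osteoporosis frequencies under Importance of Knowledge to be gained that most candidates fall in the band. Those figures are not specific to the hip and do not support a share.

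The conclusion assumes that hip joints and total hip mean the same site, and that no page unavailable to this review, such as the title and signature pages, names a controlling list. Nothing here says which hip value is right.

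**What to change.** Issue one amendment with a single controlling eligibility list. Have both existing sets of criteria, the iDXA paragraph and the fracture-protection paragraph refer to it instead of restating limits. In that list the sponsor's clinicians reconcile the hip limit, name the site measured, and join the hip, knee and total body limits with an explicit 'or'. The unnumbered osteoporosis wording in Human Subject item 3 and under Limitations and Alternatives should point to the same list.

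The same amendment should reconcile the kidney stage, the calcium limit and its unit, the pulse width of the stimulation test, and the 25(OH)D limit. The last has to be settled between below 41 and above 40 before it is carried into the Human Subject lists.

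The cost is one protocol amendment with no added procedures. The eligible pool may change with the values chosen; the documents do not allow the size of that change to be computed.
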